An analysis update will be performed when the last patient discontinued from the trial and once all patients have been randomized and have been followed-up for at least 24 months. An analysis update may be subsequently performed.

Statistical Analysis Plan (SAP) BNT111-01

Page 30 of 78 Version: Final v7.0 Date: 05Mar2024

Data up to and including the clinical cut-off date will be taken into account for the statistical analysis.

All analyses will be conducted using SAS® version 9.4 or higher.

Baseline is defined as last non-missing value prior to the first dose of trial treatment at C1D1. Assessments performed at C1D1 will be considered for baseline value, unless there is evidence the assessment was performed after trial treatment had been administered. For the add-on treatment if the baseline visit and AOC1D1 are on the same day, the assessment only needs to be taken once. In this case the AOC1D1 would be considered as the baseline value, unless there was evidence that the assessment was done after treatment had been administered.

To identify the baseline value, generally, if there are multiple assessments available for a particular day, the assessment that is closest to the day (and time if collected) of the first dose of the trial treatment (i.e., BNT111 or cemiplimab) will be used as the baseline value in the summary/analyses.

Multiple values at post-baseline visits: if there are multiple post-baseline assessments available within a visit/day, the first value and corresponding date/time will be considered.

Change from baseline will be calculated as follows:

Change from baseline = post-baseline assessment value – baseline assessment value.

If either the baseline or post-baseline assessment value is missing, the change from baseline is set to missing as well.

Duration (Other than "trial treatment duration" defined in Section 8.5.1) will be calculated as follows:

Duration = last observation date - first observation date + 1

For conversion of days to months or years the following rules will be applied:

- 1 month = 30.4375 days
- 1 year = 365.25 days

Trial Day and Treatment Day are defined as follows:

- Trial day:
 - If assessment date < randomization date then trial day = assessment date randomization date
 - If assessment date >= randomization date then trial day = assessment date randomization date + 1
- Treatment Day = treatment date date of first dose +1

That is, trial day 1 indicates the date of treatment initiation.

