All trial data will be presented at the visit as collected in the eCRF. No windowing of data for the purposes of assigning to a visit will occur.

Statistical Analysis Plan (SAP) BNT111-01

Page 31 of 78 Version: Final v7.0 Date: 05Mar2024

Unscheduled assessments will be included in the analysis of efficacy endpoints for tumor response, time to event endpoints and shift from baseline to worst NCI-CTCAE Grade laboratory summary tables. All other unscheduled assessments will be listed only and not included in summaries/analysis.

If there is a difference between randomized and actual strata at randomization then the randomized strata will be used for analyses. A summary of randomized and actual strata at randomization will be presented. If there is a notable difference between the two summaries, then a sensitivity analysis for the primary endpoint will be considered.

Handling missing Data:

For the purposes of assigning treatment-emergent flag for AEs, partial or missing AE dates will be handled as follows:

- If the day of the month is missing, the onset day will be set to the first day of the
 month unless it is the same month and year as the first trial treatment. In this case,
 in order to conservatively report the event as treatment-emergent, the onset date will
 be assumed to be the date of the first trial treatment.
- If the onset day and month are both missing, the day and month will be assumed to be January 1, unless the event occurred in the same year as the first trial treatment.
 In this case, the event onset will be assumed to be the day and month of treatment in order to conservatively report the event as treatment-emergent.
- A completely missing onset date will be assumed to be the day of the first trial treatment.
- If an AE has a partial start date that is in the same month/year as the first dose of trial treatment, then the AE will be reported as treatment-emergent. If an AE has a missing start date, then the AE will be reported as treatment-emergent.

For the purposes of assigning treatment-emergent flag for irAEs, partial or missing irAE dates will be handled as follows:

- If the day of the month is missing, the onset day will be set to the first day of the
 month unless it is the same month and year as the first trial treatment of cemiplimab.
 In this case, in order to conservatively report the event as treatment-emergent, the
 onset date will be assumed to be the date of the first trial treatment of cemiplimab.

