8.5.2 Adverse events

Adverse events (AEs) will be coded using Medical Dictionary for Regulatory Activities (MedDRA®) coding system version 23.1 or later to get a System Organ Class (SOC) and Preferred Term (PT) for each AE and graded for severity using NCI CTCAE v5.0. In case a patient has an AE with missing relationship status, the event will be assumed to be related and associated with the treatment received in the summaries (will be listed as collected in the listings). No imputation for missing NCI-CTC grades will be performed.

TEAEs for randomized treatment

A treatment-emergent AE (TEAE) is defined as any AE with an onset date on or after the first administration of trial treatment (if the AE was absent before the first administration of

Statistical Analysis Plan (SAP) BNT111-01

Page 46 of 78 Version: Final v7.0 Date: 05Mar2024

trial treatment) or worsened after the first administration of trial treatment (if the AE was present before the first administration of trial treatment). AEs with an onset date more than 90 days after the last administration of trial treatment will be considered as treatment emergent only if assessed as related to trial treatment by the investigator, prior to start of Add-on treatment, if applicable, whichever comes first.

An AE will be considered TE for the randomized treatment if it started within 90 days of last dose of randomized treatment or until start of add-on treatment whichever comes first.

Add-on TEAEs

Treatment-emergent for add-on treatment is defined as any AE with an onset date on or after the first administration of add-on treatment (if the AE was absent before the first administration of add-on treatment) or worsened after the first administration of the add-on treatment (if the AE was present before the first administration of add-on treatment). AEs with an onset date more than 90 days after the last administration of add-on treatment will be considered as TE only if assessed as related to add-on treatment by the investigator.

TEAEs for both randomized and add-on treatment

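### AE onset imputation ignores the first add-on dose, so incomplete dates in the month or year of add-on start, and fully missing dates, are counted under monotherapy

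*SAP*

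**What the plan says.** SAP 8.1, under the handling of missing data, has three cases for AEs in general.

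- Day missing: "If the day of the month is missing, the onset day will be set to the first day of the" month. If that is also the month and year of the first trial treatment, onset will instead "be assumed to be the date of the first trial treatment".
- Day and month missing: the date is "assumed to be January 1, unless the event occurred in the same year as the first trial treatment", in which case the first-treatment date is used.
- Nothing recorded: "A completely missing onset date will be assumed to be the day of the first trial treatment".

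None of the three mentions the first add-on dose. The baseline text in the same section speaks "of the first dose of the trial treatment (i.e., BNT111 or cemiplimab") and ties it to Cycle 1 Day 1. Add-on dosing is named separately throughout, so first trial treatment cannot fairly be read as first add-on dose.

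SAP 8.5.2 closes the randomized period at 90 days after the last randomized dose "or until start of add-on treatment whichever comes first". It opens the add-on period with this definition: "Treatment-emergent for add-on treatment is defined as any AE with an onset date on or after the first administration of add-on treatment". An AE already present also counts if it worsened after that dose. Randomized, add-on and combined TEAEs are each summarized.

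Immune-related AEs have a separate rule in SAP 8.1, anchored on the first cemiplimab dose.

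**The concern.** The period to which an AE belongs is decided by its onset date. SAP 8.1 cuts the other safety data at the first add-on dose but exempts AEs from that cut, leaving them to the definitions in 8.5.2. An imputation that knows only the first trial dose can pull an event from after add-on start to a date before it. It never pushes an event the other way, because every imputed date is either the first trial dose or the first day of the recorded month or year.

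Two reported quantities are affected. The single-agent safety profiles, a secondary objective, would gain events that occurred on the combination. The add-on tables, which describe the combination after crossover, would lose them. The imputation is meant to err towards counting an event against treatment. For the add-on table it errs towards leaving the event out.

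**Working it through.** The documents give no figure to reproduce, so the check applies the written rules to dates.

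**Inputs.** The three imputation cases come from SAP 8.1 and the period split from SAP 8.5.2. Let F be the first trial dose and A the first add-on dose. An event counts as monotherapy when its imputed onset is before A.

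**Worked dates (illustrative).** All events below truly began after A.

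| F | A | True onset | Day missing | Day and month missing |
|---|---|---|---|---|
| 10 Mar 2022 | 12 Jul 2022 | 20 Jul 2022 | 1 Jul 2022, monotherapy (wrong) | 10 Mar 2022, monotherapy (wrong) |
| 10 Mar 2022 | 12 Jul 2022 | 20 Aug 2022 | 1 Aug 2022, add-on | 10 Mar 2022, monotherapy (wrong) |
| 10 Mar 2022 | 12 Jul 2022 | 5 Feb 2023 | 1 Feb 2023, add-on | 1 Jan 2023, add-on |
| 10 Oct 2022 | 12 Feb 2023 | 20 Feb 2023 | 1 Feb 2023, monotherapy (wrong) | 1 Jan 2023, monotherapy (wrong) |
| 10 Oct 2022 | 12 Feb 2023 | 20 May 2023 | 1 May 2023, add-on | 1 Jan 2023, monotherapy (wrong) |
| 10 Oct 2022 | 12 Feb 2023 | 5 Feb 2024 | 1 Feb 2024, add-on | 1 Jan 2024, add-on |

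A completely missing onset becomes F in every row, hence monotherapy (wrong).

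**General conditions.**

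- (a) Day missing: wrong only when the recorded month is the month of A, unless A is the 1st.
- (b) Day and month missing: wrong when the recorded year is that of F or of A, unless A falls in a later year than F and is 1 January. If an event after A lies in the year of F, then A lies in that year too, so the year of A is sufficient for writing a rule.
- (c) Nothing recorded: always wrong.

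**Share of true post-add-on AEs moved back, given an incomplete date.** Assume add-on starts are spread evenly over the calendar and AE onset is uniform over the L days from add-on start.

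- Day missing, 30-day month: the average over start days 2 to 30 of the days left in the month, divided by L, is (1 + 2 + … + 29)/(30 × L) = 29/(2L).
- Day and month missing, 365-day year: 1 − (L − 1)/730, less 1/365 for starts on 1 January.

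| L (days) | Day missing | Day and month missing | Nothing recorded |
|---|---|---|---|
| 42 | 29/84 = 34.5% | 94.1% | 100% |
| 90 | 29/180 = 16.1% | 87.5% | 100% |
| 180 | 29/360 = 8.1% | 75.2% | 100% |
| 365 | 29/730 = 4.0% | 49.9% | 100% |

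A simulation with add-on starting 84, 126 or 180 days after first dose gave about 35%, 16–17%, 8% and 4% with the day missing. With day and month missing it gave about 94%, 87–88%, 75% and 50%. The length of monotherapy made almost no difference. These are shares of AEs whose dates are already incomplete, not of all AEs.

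**The case against.** Several limits stand.

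- **Few dates should be incomplete.** Protocol 10.3.1.7 requires the start date and time of each AE, and 10.11.3 provides for data queries.
- **No event leaves the report.** A shifted AE remains treatment-emergent and appears in the combined summary. Relatedness is assessed and tabulated per drug, so attribution to BNT111 survives. The worsening clause returns some events to the add-on table, though not a new, transient reaction.
- **Safety summaries are descriptive**, and no formal comparison between groups depends on them.

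A reader might infer more than this, in three ways. One is that every partially dated AE after add-on start is moved back; the worked dates show that later months (day missing) and later years (day and month missing) stay in add-on.

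Another is that BNT111 first-dose reactions would be hidden in the cemiplimab arm. Protocol 2.3.1 puts hypotension within 4 to 6 hours of dosing, and 8.2.3 requires at least 6 hours of observation after the first three BNT111 administrations, so these events are unlikely to lack a date. Nor does the second dose, on add-on day 8, always fall in the month of add-on start: in a 30-day month, starts on days 24 to 30 (7 of 30) place it in the next month.

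The third is that cemiplimab reactions in Arm 2 are misplaced to the same degree. There the irAE anchor, first cemiplimab, is the add-on start itself, and the irAE list in Protocol Appendix 12.1 is broad.

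**Conclusion.** The point holds in the limited form stated. Followed literally, SAP 8.1 gives the wrong period under 8.5.2 for post-add-on AEs meeting conditions (a), (b) or (c). This is a written rule with a wrong result, not merely a missing detail. The error has one direction: add-on TEAEs too low, single-agent TEAEs too high.

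The absolute size is probably small but cannot be stated, because no partial-date rate is given. The percentages above rest on even add-on starts and uniform onset; events concentrated soon after add-on start would be affected more often. The finding concerns only the general AE rule and the two period-specific tables. It does not support a claim that events are lost, that the overall safety picture is wrong, or that irAEs in Arm 2 are mishandled.

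**What to change.** Add to SAP 8.1, for the add-on treatment-emergent flag in the Add-on Treatment Set: set onset to the date of the first add-on dose when both of the following hold.

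- The known part of the onset date matches the first add-on dose in month and year (day missing) or in year (day and month missing), or the onset is completely missing.
- The AE end date is not before the first add-on dose. An ongoing AE meets this condition; say how an incomplete end date is read.

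Otherwise keep the current rule. An AE that truly began after add-on cannot have ended before it, so conditions (a) to (c) would no longer send such events to monotherapy.

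Do not use recorded causality to set the date. It is an open-label judgment, and it cannot separate the periods for the drug given in both. State whether an event dated in this way is also kept in the randomized-period table.

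The cost is a few SAP lines and minor programming. Some ongoing monotherapy AEs with ambiguous dates will be counted as add-on TEAEs, which is the conservative direction for the add-on summary and should be stated in the SAP.

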8.3 Adverse events and serious adverse events

The investigator and any qualified designees are responsible for detecting, documenting, and recording events that meet the definition of an AE or SAE and remain responsible for following up all AEs and SAEs.

8.3.1 Time period and frequency for collecting adverse event and serious adverse event information

All AEs and SAEs will be collected from the first signing of the ICF until the SFU2 visit (90 days after last trial dose or until a new anti-cancer therapy is started) at the time points specified in the SoA (Section 1.3). Additionally, in case a new anti-cancer therapy is started within 90 days after last treatment, the safety follow-up visit should be performed just prior to starting the new anti-cancer therapy. Adverse events after start of new anti-cancer therapy do not need to be reported unless a causal relationship to BNT111-01 or cemiplimab is suspected.

All SAEs (initial and follow-up reports) will be recorded and reported to the sponsor or designee within the appropriate time frame and under no circumstance should this exceed 24 h after knowledge of the event, as indicated in Section 10.3.1.10. AESIs should also be reported within an appropriate time frame (i.e., no more than 24 h after knowledge of the event).

Investigators are not obligated to actively seek AEs or SAEs after a patient has discontinued from the trial. However, if the investigator learns of any SAE, including a death, at any time after a patient has discontinued from the trial, and he/she considers the event to be reasonably related to the trial treatment or trial participation, the investigator must promptly notify the sponsor.

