10.3.1.7 Recording and follow-up of adverse events and/or serious adverse events

AE and SAE recording

The investigator needs to assess and document any AE regardless of association with the use of the trial treatment during the period of observation (refer to Section 8.3.1).

- Data pertaining to AEs will be collected during each trial visit either based on the
 patient's spontaneous description or investigator's inquiry or discovered in the
 course of examinations done during the visit, clinical significance of any sign or
 symptom needs to be evaluated by the investigator.
- Clinically significant findings need to be documented as AEs in the source data and eCRF. Findings that are evaluated and documented in the source data as not

Page 106 of 133 Version: 7.0 Date: 09 FEB 2023

clinically significant (e.g., an abnormal laboratory value without any clinical manifestation), should not be documented as AE.

- The investigator will then record all relevant AE information in the eCRF and perform an assessment on:
 - Intensity according to NCI-CTCAE v5.0
 - Seriousness
 - Outcome
 - Causal relationship of the AE to the trial treatment/trial procedure
 - Any trial treatment action and/or any other action taken
- All assessments as well as AE term (diagnosis/description), start date and time of onset, end date and time need to be documented in the eCRF.
- There may be instances when copies of medical records for certain cases are requested by the sponsor. In this case, all patient identifiers, with the exception of the patient number, will be redacted on the copies of the medical records before submission to the sponsor.
- To avoid colloquial expressions, the AE should be reported in standard medical terminology. The investigator will attempt to establish a diagnosis of the event based on signs, symptoms, and/or other clinical information. Whenever possible, the diagnosis (not the individual signs/symptoms) will be documented as the AE. If a definitive diagnosis is not possible, the individual signs and symptoms should be recorded.

Assessment of intensity

The intensity of an AE (i.e., severity of organ toxicity) will be graded according to the NCI-CTCAE v5.0. AEs that are not listed in NCI-CTCAE v5.0 should be classified according to the investigator's discretion as close as possible to NCI-CTCAE v5.0, based on the comparison with the most severe case encountered in past training and clinical experience.

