- If the onset day and month are both missing, the day and month will be assumed to be January 1, unless the event occurred in the same year as the first trial treatment of cemiplimab. In this case, the event onset will be assumed to be the day and month of treatment of cemiplimab in order to conservatively report the event as treatmentemergent.
- A completely missing onset date will be assumed to be the day of the first trial treatment of cemiplimab.

Statistical Analysis Plan (SAP) BNT111-01

Page 32 of 78 Version: Final v7.0 Date: 05Mar2024

 If an irAE has a partial start date that is in the same month/year as the first dose of trial treatment of cemiplimab, then the irAE will be reported as treatment—emergent.
 If an irAE has a missing start date, then the irAE will be reported as treatment—emergent.

For the purposes of assigning prior or concomitant flag for medications, partial or missing medication dates will be handled as follows:

- If end day is missing and month/year are non-missing, then day is the earliest of treatment end date (if month/year of treatment end date is same as the medication month/year) and the last day of the month.
- If end day/month are missing and year is non-missing, then day/month is the minimum of treatment end date (if year of treatment end date is same as the medication year) and the end of the year (31DECYYYY).
- If imputed end date is less than the start date, use the start date as the imputed end date.
- If the start date year is missing, the start date is set to one day prior to treatment start date
- If the start date year is less than the treatment start date year, then:
 - If the month is missing, the start date is assumed to be mid-year point (01JULYYYY).
 - Else if the month is not missing, the start date is assumed to be mid-month point (15MONYYYY).
- If the start date year value is greater than the treatment start date year, then:
 - If the month is missing, the start date is assumed to be the year start point (01JANYYYY).
 - Else if the month is not missing, the start date is assumed to be the month start point (01MONYYYY).
- If the start date year value is equal to the treatment start date year value:
 - If the month is missing or the month is equal to the treatment start date month, then the start date is assumed to be one day prior to the treatment start date.
 - Else if the month is less than the treatment start date month, the start date is assumed to the mid-month point (15MONYYYY).

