 - Else if the month is greater than the treatment start date month, the start date is assumed to be the month start point (01MONYYYY).

If complete end date is available and the start date assumed from the steps above is greater than the end date, then the assumed start date should be set to the end date.

Partial anti-cancer therapy start dates will be handled as follows:

Statistical Analysis Plan (SAP) BNT111-01

Page 33 of 78 Version: Final v7.0 Date: 05Mar2024

- If the start of subsequent anti-cancer therapy date is missing, this will be imputed to the date of the EOT visit.
- Missing day, month/year present: If the month/year is the same as the month/year of EOT Visit date, then impute missing start dates with EOT Visit date. Otherwise, for dates corresponding to a start date, impute with the first day of the month.
- Missing month/day, year present: If the year is the same as the year of EOT Visit date, then impute missing start dates with EOT Visit date. Otherwise, for dates corresponding to a start date, impute with the first day of the year.
- If the EOT Visit date is missing, the date of last treatment will be used for imputation.

Partial date of progression for prior cancer therapies will be handled as follows, for the derivation of the time since the first diagnosis subgroup:

- Assign the day to the 15th of the month.
- If the month/year is missing, the date of progression will not be imputed.

Partial diagnosis dates will be handled as follows, for the derivation of the time since the first diagnosis subgroup:

- Assign the day to the 15th of the month.
- If the month is missing, the initial diagnosis date is assumed to be mid-year point (01JULYYYY).
- Else if the month is not missing, the initial diagnosis date is assumed to be mid-month point (15MONYYYY).

For analysis of pharmacodynamic data:

- The actual date collected will be used. If the date is not available, the value will be considered as missing.
- The actual time of sample collection will be used. If the time is not available, the value will, at the discretion of study pharmacodynamics analysist (in consultation with BioNTech), be considered as missing or imputed to be the nominal sampling time.

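### The partial-date rules in SAP 8.1 flag an AE or irAE with an incomplete onset as treatment-emergent even when its recorded stop date precedes the reference dose

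*SAP*

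**What the plan says.** For the treatment-emergent flag, SAP 8.1 imputes AE onset as follows. If only the day is missing and the month and year match the first dose, onset becomes the first-dose date. If day and month are missing and the year matches, onset again becomes the first-dose date. With nothing recorded, "A completely missing onset date will be assumed to be the day of the first trial treatment". A closing bullet then sets the flag directly: "If an AE has a partial start date that is in the same month/year as the first dose of trial treatment", the event is treatment-emergent, and "If an AE has a missing start date, then the AE will be reported as treatment-emergent".

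The irAE bullets repeat this with a different anchor: "A completely missing onset date will be assumed to be the day of the first trial treatment of cemiplimab".

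Neither set mentions the stop date. The medication rules in the same section do consult it: "If complete end date is available and the start date assumed from the steps above is greater than the end date", the assumed start is reset to the end date.

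SAP 8.5.2 defines a TEAE as an event with "onset date on or after the first administration of trial treatment (if the AE was absent before the first administration of" trial treatment), or one that worsened after that first administration.

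**The concern.** Treating an uncertain onset as treatment-emergent is a sensible precaution when the timing is unknown. It stops being a precaution when the record shows that the event was over before dosing. Onset on or after the first dose is then excluded, and the imputation overrides a recorded fact.

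Such records can exist. Protocol 8.3.1 states that "All AEs and SAEs will be collected from the first signing of the ICF until the SFU2 visit", so events that begin and end during screening are in the database. They can also be recognised, because Protocol 10.3.1.7 requires that the "end date and time need to be documented in the eCRF".

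At stake are the counts in the TEAE tables of SAP 8.5.2, including the Grade 3 or higher and serious categories, and irAE occurrence, which is a secondary safety endpoint. For irAEs the setting is plausible: every patient has had at least 12 weeks of anti-PD-1/PD-L1 therapy, and Protocol 8.4 notes that an irAE can appear several months after the last dose. A reaction left over from earlier therapy could resolve during screening.

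**Working it through.** The plan gives no figure on this point, so there is none to reproduce. The check has three parts.

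**1. The rule applied to one record (assumed dates).** First dose 20 March 2022; AE start recorded as March 2022 with the day unknown; stop 12 March 2022.

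- SAP 8.1 as written: the month and year match the dose, so onset = 20 March and the event is treatment-emergent. The imputed onset is 8 days after the recorded stop (20 − 12 = 8).
- Same record with only the year known, or with no start date: same result.
- Same record with a partial start of February 2022: onset = 1 February, not flagged. The fault is therefore confined to a start that matches the dose month (or the year, if only that is known) or is missing.
- With the medication-style check: onset = 12 March, not flagged.

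**2. The rule against the definition.** Under SAP 8.5.2 an event qualifies by starting on or after the first dose or by worsening after it. An event that stopped on 12 March did neither. SAP 8.1 and SAP 8.5.2 therefore disagree on this record, and nothing in SAP 8.5.2 overrides the closing bullet of SAP 8.1.

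**3. Share misflagged among the affected records.** Inputs: a screening window of 21 days (Protocol 4.1.1). Assumptions: first dose equally likely on any day d of a 30-day month; true onset equally likely on each of the 21 days before dosing; a complete stop date before dosing.

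*Day missing.* The event is misflagged when its onset falls in the dose month. For a dose on day d, that covers min(d − 1, 21) of the 21 days.

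- Sum over d = 1 to 30: (0 + 1 + … + 21) + 8 × 21 = 231 + 168 = 399
- Share: 399 / (21 × 30) = 399 / 630 = 0.633

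Enumerating every first-dose date in 2022 with every onset 1 to 21 days earlier (365 × 21 = 7,665 combinations) gives 0.638.

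*Day and month missing.* The event escapes only if its onset fell in the previous calendar year, which needs a dose on 1 to 21 January: 21 + 20 + … + 1 = 231 combinations. Share misflagged: 1 − 231 / 7,665 = 0.970.

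*Start date wholly missing.* 100%, by the rule itself.

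With the end-date check added, all three shares are 0%.

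*Sensitivity of the day-missing share to the window (30-day month).*

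| Window | Calculation | Share |
|---|---|---|
| 10 days | 245 / 300 | 82% |
| 21 days | 399 / 630 | 63% |
| 28 days | 434 / 840 | 52% |

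The 28-day row reflects footnotes to the schedule of activities, which allow eligibility to be confirmed within 21 days of starting screening and treatment to begin up to 7 days later.

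**The case against.** The best defence is that the affected set is narrow. Three things must coincide: the event occurs before dosing, its onset is incomplete, and its recorded stop is before the dose. Protocol 10.3.1.7 asks for start and end dates and times, and Protocol 10.11.3 provides for queries on discrepant data. A known stop with an unknown start, inside a short and prospectively observed window, should be uncommon. This stands, and it means the percentages above are shares of a subset of unknown size.

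The direction is also safe. The SAP says it imputes conservatively, and the error can add TEAEs but cannot hide one. No formal comparison between arms is planned. The IDMC triggers rest on related events or on a Grade 5 TEAE, and a fatal event cannot have ended before the first dose. No decision rule is shown to be affected. This stands too.

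A reader might infer that the related-TEAE tables are inflated. The date rule does not set causality. Investigators judge it with timing in view, so a pre-dose event reaches those tables only if it is marked related, or if causality is missing and SAP 8.5.2 therefore assumes it related.

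A reader might also object to an onset later than the stop date because the general duration formula in SAP 8.1 would give −7 days in the example (12 − 20 + 1). But the imputation serves the flag, and SAP 8.5.2 specifies no AE-duration analysis, so no planned output would show that figure.

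What the defence does not reach is the rule itself. It is unconditional, and conservatism is no reason to discard a recorded stop date.

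**Conclusion.** The rule is wrong as written, but the matter is minor. An AE or irAE with an incomplete onset and a stop date before the reference dose is flagged treatment-emergent, contrary to the SAP's own TEAE definition and without the check the SAP applies to medications. Within that group, about 63% are misflagged when only the day is missing (52% to 82% for windows of 28 to 10 days), about 97% when day and month are missing, and 100% when there is no start date. All but the last figure rest on uniform timing of onset and first dose.

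The number of patients affected cannot be derived, because the documents do not say how often AE start dates are incomplete. The consequence is over-counting in the TEAE tables.

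It would be going too far to say that screening events in general are counted as treatment toxicity. Screening events with complete dates are classified correctly, and entering a TEAE table is not the same as being attributed to treatment.

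**What to change.** Add one sentence to both the AE and the irAE rules in SAP 8.1: if the stop date, or its known part, shows that the event ended before the reference dose, the event is not treatment-emergent relative to that dose, and an imputed onset may not be later than a complete stop date.

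Three details matter.

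- **Name the reference dose.** It is the first trial treatment for AEs and the first cemiplimab dose for irAEs. These differ for Arm 2 patients who enter add-on therapy, whose first cemiplimab dose follows a period of BNT111 monotherapy.
- **Make the closing bullet of each rule subject to the exception.** That bullet sets the flag directly, so capping the imputed date alone would leave the conflict in the text.
- **Limit partial stop dates to clear cases.** A stop known only as February 2022 with a dose on 20 March 2022 settles the matter. A stop known only as March 2022 does not, and the existing conservative rule should then apply. This goes slightly beyond the medication rule, which uses complete end dates only.

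The cost is one sentence per rule and about one line of derivation code. It uses dates already collected and touches no efficacy analysis.
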